7.5. COVID-19 Vaccine

Hepion in no way wishes to preclude subjects from receiving the COVID-19 vaccine. However, in order to minimize potential adverse events associated with the vaccine, if possible, the subject should try to receive their second dose of the vaccine seven days prior to the commencement of receiving study drug (Day 1) or receive their first dose of the vaccine 96 hours after their last dose on Day 28.

Enrolled study subjects who have an opportunity to be vaccinated against COVID-19 should do so. Study subjects will be permitted to continue on the study if they receive the COVID-19 vaccine.

The COVID-19 vaccine should be recorded in the subject's Concomitant Medications CRF page if the subject receives the vaccine after consent and through Day 42/EOS.

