7.7.3. Pharmacokinetic Criteria for Dose Adjustment

Dose adjustment is not available for subjects in Cohort A receiving 75 mg of CV431 QD. If a patient demonstrates adverse events that trigger the need for stopping, that patient will be stopped and an additional patient will be started on the same dose unless the study data indicates a problem with the dose level as recommended by the DSMB. Subjects in Cohort C, receiving 225 mg of CRV431 QD, experiencing a drug exposure related Grade 3,4 or 5 CTCAE can have a dosage reduction to 150 mg of CRV431 once daily.

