8.3. Subject Withdrawal Criteria

8.3.1. Early Termination of Subjects from the Study

Subjects who discontinue the study should complete all scheduled safety assessments at the Early Termination Visit. If an Early Termination Visit and a scheduled visit coincide, procedures for both visits should be completed, without duplication. Subjects must discontinue the study for the following reasons:

- Subject withdraws consent;
- Subject unwilling or unable to follow study procedures, per judgment of the investigator;
- Investigator, sponsor, or Regulatory Authority judge that further dosing with study drug would be harmful to the subject;
- Subject experiences an SAE that is judged, by the investigator and the sponsor, to be related to study drug;
- Subject experiences a Grade 3 CTCAE AE judged, by the investigator and the sponsor, to be related to study drug;
- Subject experiences a Grade 4 CTCAE AE judged, by the investigator and the sponsor, regardless of the relation to study drug;
- Subject experiences a Grade 3 or Grade 4 CTCAE laboratory abnormality judged by the investigator and the sponsor, to be related to study drug except for asymptomatic elevations in cholesterol or triglycerides which are accepted;

- Subject with normal ALT and bilirubin at baseline who experiences confirmed, non-cholestatic ALT $>3 \times$ ULN and bilirubin $>2 \times$ ULN OR subjects with elevated ALT at baseline who experiences confirmed, non-cholestatic ALT $>10 \times$ baseline value and bilirubin $>2 \times$ ULN;
- Subject experiences a confirmed,
 - QTcF interval 500 msec;
OR
 - QTcF interval change from baseline ≥ 60 msec that has an absolute value ≥ 480 msec. The value of an individual ECG time point is the average of the triplicate values
 - “confirmed” is defined as the abnormality duplicated, at least 1 hour after the abnormality is first noted, by the results of a set of 3 ECGs performed in triplicate, at least 5, but not more than 10 minutes between each assessment;
- Subject experiences any hepatic AE or SAE judged by the investigator or sponsor as DILI and to be related to study drug and not to the subject’s underlying NASH.

Subjects who discontinue the study due to the safety stopping criteria will be replaced if the investigator and sponsor agree and the criteria outlined in Section 7.5 are not violated. Subjects who discontinue the study for non-safety reasons may be replaced.

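### Section 7.7.3 lets Cohort C subjects with drug-related Grade 3 or 4 events continue at 150 mg, Section 8.3.1 requires them to discontinue, and no clause says which rule governs

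*Combined protocol and SAP*

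**What the plan says.** Protocol Section 7.7.3 gives Cohort A no dose adjustment. It says that a patient whose adverse events trigger stopping is stopped, and then that Cohort C subjects "experiencing a drug exposure related Grade 3,4 or 5 CTCAE can have a dosage reduction to 150 mg of CRV431 once daily".

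Section 8.3.1 introduces its list with "Subjects must discontinue the study for the following reasons". Three items matter here:

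- For Grade 3 adverse events, attribution to the drug is needed: "Subject experiences a Grade 3 CTCAE AE judged, by the investigator and the sponsor, to be related to study drug".
- For Grade 4 adverse events, cause is irrelevant: "Subject experiences a Grade 4 CTCAE AE judged, by the investigator and the sponsor, regardless of the relation to study drug".
- Laboratory findings have an item of their own: "Subject experiences a Grade 3 or Grade 4 CTCAE laboratory abnormality judged by the investigator and the sponsor, to be related to study drug". Rises in cholesterol or triglycerides without symptoms do not count.

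A related SAE is also on the list, as is a liver event: "Subject experiences any hepatic AE or SAE judged by the investigator or sponsor as DILI and to be related to study drug". The liver item adds that the event must not be attributed to the underlying NASH.

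Section 7.7.1 names related Grade 3 or higher events, any Grade 4 event and related SAEs as stopping criteria for an individual subject. Their stated consequence is a halt to dosing at every site until the DSMB, Medical Monitor and sponsor have reviewed the safety data. If dosing is then judged safe, a substantial amendment is submitted, where applicable.

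On replacement after a safety discontinuation, 8.3.1 sets the condition that "the criteria outlined in Section 7.5 are not violated". The section with that number is "7.5. COVID-19 Vaccine".

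**The concern.** For the same Cohort C subject with the same event, one section permits continued drug at a lower dose and another requires discontinuation. A protocol can offer dose reduction after a severe related event, or it can withdraw the subject. It should not do both without saying when each applies. Once a hold is lifted, about 10 sites could treat like cases differently, and one of the two written instructions keeps a subject on drug after a Grade 3 or 4 event attributed to it. This is the higher of the two dose levels in a study whose primary objectives include safety and tolerability.

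**Working it through.** The plan states no figure on this point, so the check sets the clauses side by side for a Cohort C subject.

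| Event | 7.7.3 | 8.3.1 | Result |
|---|---|---|---|
| Related Grade 3 AE | may go to 150 mg | must discontinue | conflict |
| Related Grade 4 AE | may go to 150 mg | must discontinue, whatever the cause | conflict |
| Related Grade 3 or 4 laboratory abnormality | may go to 150 mg | must discontinue, lipid exception aside | conflict |
| Related Grade 5 event | may go to 150 mg | not listed by grade; reached only as a related SAE | 150 mg has no meaning |

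**Attribution.** The phrase in 7.7.3 about drug exposure may be narrower than relatedness to study drug in 8.3.1. If so, it describes a subset of related events, and 8.3.1 still applies to all of them. This assumes that attribution is judged in the same way for both sections: 8.3.1 names the investigator and sponsor, and 7.7.3 names nobody.

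**What is left if 8.3.1 governs.** Within the grades that 7.7.3 names, the only exception in 8.3.1 is for asymptomatic lipid laboratory rises. The 150 mg option would then be almost empty. If 7.7.3 governs instead, a mandatory rule is overridden without saying so.

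**Precedence.** Section 7.7.3 does not cite 8.3.1. The one pointer from 8.3.1 to the stopping rules leads to the vaccine section. The same stale number appears twice in the synopsis methodology and once in Section 7.1.3. The holds and stops in 7.7.1, 7.7.2 and 7.7.2.1 act on the study and do not say whether the affected subject may resume. None of the sections compared shows a redaction.

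**Reach.** Cohort C has 12 planned subjects: 12/36 = one third of the study, and 12/24 = one half of those assigned to CRV431.

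**Liver events (secondary and weaker).** The hepatic branch of 7.7.1 opens with events already judged related and defines DILI by aminotransferase thresholds. For persistent elevation on repeat testing it asks for close observation, or that discontinuation be considered, or both. Section 8.3.1 requires discontinuation once the event is judged DILI, related to study drug and not due to underlying NASH. The gap is that 7.7.1 never says its optional step ends when that judgment is made.

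**The case against.** The best defence is that the protocol already blocks the harmful route. One related Grade 3 event, or any Grade 4 event, halts dosing everywhere, and restarting may need a substantial amendment in which the subject's status could be settled. Treatment lasts 28 days, and missing more than 2 consecutive doses is itself a ground for considering discontinuation, so a subject held for review may never reach 150 mg. This stands as a limit on risk. It does not remove the conflict: the amendment is required only where applicable, missed doses only prompt a decision, and 7.7.3 still expressly offers that subject more drug.

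A second defence is that the sentence in 7.7.3 about stopping a patient is general and so favours 8.3.1. That reading is open. But the sentence follows the Cohort A rule, and the Cohort C sentence comes after it as a different outcome. Nor is the difference between the cohorts a fault in itself: Cohort A takes a single 75 mg capsule and has no lower step.

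A third defence concerns liver events. Section 7.8 speaks of early signs of possible DILI, so 7.7.1 can be read as work-up before the final judgment that 8.3.1 requires. This is plausible, which is why the liver limb is secondary.

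A reader might also infer that Grade 5 is a third working conflict. It is not: nobody continues dosing after death, and the Grade 5 rule in 7.7.2.1 is a study-level stop. Nor do the texts show drug continuing after a serious event as such, because Section 11.4 separates severity from seriousness.

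**Conclusion.** The protocol contradicts itself on whether a Cohort C subject with a drug-related Grade 3 or 4 event may stay on CRV431, and it should be corrected. The conflict potentially covers the 12 planned Cohort C subjects. How many would meet it cannot be estimated, because the visible text gives no expected event rates. A reader might use the Cmax values in Section 5.3 to argue that 150 mg is barely a reduction. Two dose levels, with no AUC in the visible text, do not establish that, and the point does not need it.

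The mention of Grade 5 is a drafting error. The liver-event wording is a lesser ambiguity, not a flat contradiction. Immediate risk is limited by the dosing holds. The conclusion rests on the current wording and on the assumption that no redacted text elsewhere sets precedence.

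**What to change.** Make four wording changes in one amendment:

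1. In 7.7.3, replace the Cohort C sentence with: *Subjects in Cohort C may have the dose reduced to 150 mg once daily for a drug exposure related event that does not meet a discontinuation criterion in Section 8.3.1; a subject who meets an 8.3.1 criterion is discontinued and does not resume study drug when a pause is lifted.* This also removes the Grade 5 error. If the sponsor wants 150 mg available for particular non-hepatic Grade 3 events, name them as an explicit exception in both 8.3.1 and 7.7.1.
2. In 7.7.1, add: *If the event is judged to be DILI, related to study drug and not to underlying NASH, study drug is discontinued as in Section 8.3.1.*
3. State that 8.3.1 governs the individual subject, leaving the study-level pauses and stops in 7.7.1, 7.7.2 and 7.7.2.1 unchanged.
4. Change the stopping-rule reference from Section 7.5 to Section 7.7 in the synopsis methodology (two places), Section 7.1.3 and Section 8.3.1.

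No visits or samples are added. The sponsor should note that edit 1 leaves the 150 mg option mainly for events below Grade 3. Some Cohort C subjects who might have continued would be withdrawn and their later PK and biomarker data lost. Section 8.4 allows them to be replaced, with the same treatment assignment, unless a stopping rule precludes it.

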7.2. Number of Subjects

A total of 36 adult male or female subjects with presumed NASH F2/F3 will be enrolled. Of the 36 subjects, 12 subjects will be enrolled in Cohort A to receive 75mg of CRV431, 6 subjects will be enrolled in Cohort B to receive the matching placebo of Cohort A, 12 subjects will be enrolled in Cohort C to receive 225mg of CRV431 and 6 subjects will be enrolled in Cohort D to receive the matching placebo of Cohort C.

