7.7.2.1. Study Stopping Criteria

Study will be stopped and a review of all available safety information is performed by the DSMB, Medical Monitor, and Sponsor if any of the below criteria is met:

- ≥ 1 subject develops a Grade 5 CTCAE adverse event attributed to CRV431
- ≥ 2 subjects develop a Grade 4 CTCAE adverse event attributed to CRV431
- ≥ 3 subjects develop the same Grade 3 CTCAE adverse event attributed to CRV431

The study may be restarted depending on the specific AE, relationship to the study drug and with the agreement of the DSMB, Medical Monitor and Sponsor.

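### Section 7.7.3 allows a Cohort C subject with a related Grade 3 or 4 event to continue at 150 mg, while section 8.3.1 requires that subject to leave the study

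*Combined protocol and SAP*

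**What the plan says.** Section 7.7.3 rules out dose adjustment in Cohort A. It then says that a patient whose adverse events call for stopping is stopped and another is started at the same dose, unless the data point to a problem with that dose. For Cohort C it says that a subject "experiencing a drug exposure related Grade 3,4 or 5 CTCAE can have a dosage reduction to 150 mg of CRV431 once daily".

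Section 8.3.1 introduces its list with "Subjects must discontinue the study for the following reasons". Three entries matter here:

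- The entry for Grade 3 events reads "Subject experiences a Grade 3 CTCAE AE judged, by the investigator and the sponsor, to be related to study drug".
- The entry for Grade 4 events drops the condition on cause and reads "Subject experiences a Grade 4 CTCAE AE judged, by the investigator and the sponsor, regardless of the relation to study drug".
- The entry for serious events turns on seriousness instead of grade and reads "Subject experiences an SAE that is judged, by the investigator and the sponsor, to be related to study drug".

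A further entry covers related Grade 3 or 4 laboratory abnormalities, "except for asymptomatic elevations in cholesterol or triglycerides which are accepted". That is the only exception in the grade-based entries. The section does not mention Cohort C, 150 mg or dose reduction.

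Two other rules bear on the point. Under 7.7.1, one related AE of Grade 3 or higher, one Grade 4 AE of any cause, or one related SAE halts dosing at all sites until the DSMB, Medical Monitor and Sponsor have reviewed the safety data. If further dosing is then judged safe, a substantial amendment is submitted where applicable. Under 7.7.2.1 the study stops once at least "1 subject develops a Grade 5 CTCAE adverse event attributed to CRV431".

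**The concern.** An event caused by exposure to the drug is an event related to the drug. The Grade 3 and 4 AEs for which 7.7.3 offers a lower dose are therefore the ones for which 8.3.1 requires withdrawal. One section keeps the subject on active treatment and the other removes the subject. This arises at the higher dose, in a trial whose first primary objective is safety and tolerability.

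The data differ as well. Under 8.3.1 the subject has an Early Termination Visit and is replaced if the investigator and sponsor agree. Under 7.7.3 the subject stays in Cohort C and supplies Day 28 PK and biomarker samples at 150 mg.

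**Working it through.** There is no plan figure to reproduce. The check is a comparison of the rules, followed by a small calculation of size.

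**Step 1: the same subject under both sections.**

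| Event in a Cohort C subject | 7.7.3 | 8.3.1 | Result |
|---|---|---|---|
| Exposure-related Grade 3 AE | may continue at 150 mg | must leave, if investigator and sponsor judge it related | conflict |
| Exposure-related Grade 4 AE | may continue at 150 mg | must leave, whatever the cause | conflict |
| Exposure-related Grade 5 event | may continue at 150 mg | fatal, so no dosing decision remains; 7.7.2.1 stops the study | entry has no use |
| Asymptomatic Grade 3 or 4 cholesterol or triglyceride laboratory finding | may continue at 150 mg | exempt under the laboratory entry | no conflict |

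A Grade 3 or 4 event that is also serious and related is caught a second time by the SAE entry. Where 8.3.1 intends an exception it writes one, as it does for lipids, so an unwritten exception for dose reduction cannot be assumed.

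**Step 2: does 7.7.1 reconcile them?** It halts dosing and sets the route by which dosing in the study may restart. It does not say that a subject who met a mandatory withdrawal reason may come back, and 7.7.3 does not refer to it.

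**Step 3: does the stopping sentence within 7.7.3 reconcile them?** It follows directly on the Cohort A sentence. If it is general, 7.7.3 gives way to the stopping rules and the Cohort C sentence has almost nothing left to act on. If it covers Cohort A only, the conflict stands. The text does not settle which.

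**Step 4: is the route usable?** Yes. Section 7.3 makes up 225 mg from three 75 mg capsules, so 150 mg is two.

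**Step 5: size.** Section 7.2 gives the number concerned: "12 subjects will be enrolled in Cohort C to receive 225mg of CRV431".

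- One subject as a share of the arm: 1/12 = 8.3%.
- Reduced dose as a share of the assigned dose: 150/225 = 67%.
- Chance that at least one of 12 subjects has a qualifying event: 1 − (1 − p)^12. The documents give no p, so these values are assumptions:
  - p = 1%: 1 − 0.99^12 = 11%
  - p = 3%: 1 − 0.97^12 = 31%
  - p = 5%: 1 − 0.95^12 = 46%

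These are chances that the question arises. The chance that someone in fact continues at 150 mg is lower, because the 7.7.1 review comes first, and it cannot be computed from the documents.

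**The case against.** The strongest reply is that no one is put at immediate risk. The 7.7.3 wording is a permission and the 8.3.1 wording is an obligation, so a site that withdraws the subject breaches neither. A reader might infer that a site could move a subject straight from a Grade 4 event to 150 mg. The documents do not support that: the event itself triggers the 7.7.1 halt at all sites, and dosing waits for the review and, where applicable, an amendment. This part of the reply stands and lowers the severity.

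It does not remove the conflict. Permission to do what another section forbids is still inconsistent, and the question returns once the review allows dosing to restart.

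A second reply is that exposure-related may be meant more narrowly than drug-related. A narrower class still lies inside the wider one. One small gap is real: 8.3.1 needs the investigator and the sponsor both to judge a Grade 3 AE related, while 7.7.3 does not say who judges. If they disagree, the Grade 3 entry may not apply. Grade 4 is unaffected.

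**Conclusion.** The inconsistency is confirmed for related Grade 3 and all exposure-related Grade 4 AEs in Cohort C, and Grade 5 in 7.7.3 is a drafting error. The finding rests on readable current text and does not depend on the assumed event rates. Because of the 7.7.1 halt and the compliant path through 8.3.1, it is a correction to make by amendment and falls short of a must-fix.

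Two stronger readings should be resisted.

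- A reader might infer that the plan has no rule for analysing a subject reduced to 150 mg. That cannot be shown. The PK population (protocol 12.2.1, SAP 4.2.1) already requires sufficient compliance and an evaluable profile, and SAP 7.1 summarises total exposure, doses and capsules. Protocol 12.3, parts of 10.4, and SAP 6.2 and 6.3 are redacted. No readable rule names the 150 mg case, and SAP Appendix B puts the biomarker tables on the Safety Set, which has no compliance condition.
- A reader might infer that 7.7.1, 7.7.2 and 7.7.2.1 also contradict one another. They count different things: 7.7.2 counts related Grade 3 or 4 AEs within one system organ class, while 7.7.2.1 counts Grade 4 AEs in any class or the same Grade 3 AE. Overlapping triggers that all lead to review are not opposite instructions.

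**What to change.** Choose one of two wordings:

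1. Withdraw the 150 mg continuation in 7.7.3 for every event that 8.3.1 lists as mandatory discontinuation. Since 7.7.3 covers only Grades 3 to 5, this leaves it very little to act on.
2. Keep it, and write it into 8.3.1 as an explicit exception that names the grades covered and applies only after the 7.7.1 review by the DSMB, Medical Monitor and Sponsor.

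In both cases delete Grade 5 from 7.7.3, and say whether its stopping sentence applies to Cohort C. Under option 2, also state how a subject reduced to 150 mg enters the 225 mg Day 28 PK and biomarker summaries, unless redacted text already does so.

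As an editorial matter, the references to Section 7.5 for stopping rules (Synopsis, 7.1.3, 8.3.1) should point to 7.7, since 7.5 now covers the COVID-19 vaccine.

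The cost is a wording amendment to 7.7.3 and 8.3.1 and, under option 2, a sentence on analysis. It needs no extra subjects, visits or procedures, and the study-wide halt in 7.7.1 stays as it is.

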7.8. Close Observation

Upon detection and confirmation of early signs of possible DILI (see Section 7.7.1), close observation should be initiated immediately.

Close observation will include the following:

- Repeating liver enzyme and serum bilirubin tests 2 or 3-times weekly. The frequency of retesting can decrease to once a week or less if abnormalities stabilize or the trial drug has been discontinued and the subject is asymptomatic;
- Obtaining a more detailed history of symptoms and prior or concurrent diseases;
- Obtaining a history of concomitant drug use including non-prescription medications and herbal and dietary supplement preparations, alcohol use, recreational drug use, and special diets;

- Ruling out acute viral hepatitis types A, B, C, D, and E, autoimmune or alcoholic hepatitis, hypoxic/ischemic hepatopathy, and biliary tract disease;
- Obtaining a history of exposure to environmental chemical agents;
- Obtaining additional tests to evaluate liver function, as appropriate (e.g., INR, direct bilirubin);
- Consider gastroenterology or hepatology consultations;
- Consider liver biopsy.

7.9. Criteria for Study Termination

Conditions may arise during the study that could prompt the study to be halted. Conditions that may prompt such considerations include, but are not limited to, the following:

- The discovery of unexpected, serious, or unacceptable risk to subjects enrolled in the study;
- A decision on the part of the sponsor or regulatory authority to suspend, discontinue, or shorten the study
- Study conduct at a study site may warrant termination under conditions that include the following:
 - Failure of the site to enroll eligible subjects into the study;
 - Failure of the investigator to comply with FDA, country-specific, or local regulations;
 - Submission of false information from the research facility to the sponsor, the clinical Monitor, or a regulatory authority;
 - Insufficient adherence to protocol requirements;
 - A conflict of interest on the part of the investigator, his/her institution, or site personnel that would negatively impact the integrity of the clinical trial;
 - Institution, site, investigator, or IRB/ICE under investigation for cause by a regulatory agency.

